#### 7.4 Follow up Procedures

The outcome of the health surveillance will be shared via standard email with each participant and (if they consent) their line manager. The study manager or chief investigator will send the email correspondence (outlined below) to participants as soon as practicable following the assessment, ideally this will be within a 1-3 week timeframe. There are four possible outcomes:

- 1. Questionnaire negative, nurse's photograph assessment of absent dermatitis (true negative): hand dermatitis absent. Participant will be informed.
- 2. Questionnaire negative, nurse's photograph assessment of hand dermatitis present (discordant case). Photographs will be sent to dermatologists. If dermatologists agree that dermatitis is present, this will be considered a false negative case and the participant will be encouraged to use the standard email as supporting evidence in which to self-refer themselves to their local occupational health team for further management or to follow local arrangements. If dermatologists agree no dermatitis is present, this will be noted as a true negative case, and the participant will be informed.
- 3. Questionnaire positive, nurse's photograph assessment of absent dermatitis (discordant case). Photographs will be sent to dermatologists. If dermatologists agree dermatitis is present, this will be noted as a true positive case, and the participant will be encouraged to use the standard email as supporting evidence in which to self-refer themselves to their local occupational health team for further management If dermatologists agree dermatitis is not present, this will be considered a false positive case, and the participant will be informed.
- 4. Questionnaire positive and nurse's photograph assessment of present dermatitis (true positive): hand dermatitis present. The participant will be encouraged to self-refer themselves to their local occupational health team for further management or to follow other local arrangements.

No other follow-up procedures relating this study will be delivered beyond notification of the assessment outcome.

# 8 END OF STUDY DEFINITION

We define the end of study as occurring when all data is entered, queries resolved and database locked.

# 9 ASSESSMENT OF SAFETY

This study is deemed low risk and no serious adverse events (SAEs) or safety issues are expected to arise during conduct of this study.

While the participants assessed as having hand dermatitis (positive case) will be strongly recommended to seek follow-up confidential advice and management from their local occupational health department, general practitioner (GP) or pharmacy as soon as possible, the researchers are unable to mandate that such action is taken by participants. However, as per existing NHS staff policy and statutory regulation, if staff suspect they may have hand dermatitis then they are expected to report it to their employer, therefore the onus is on the participants to fulfil this requirement.

## 9.1 Ethics & Regulatory Approvals

This study is exempt from the requirement to obtain research ethics approval since it is recruiting NHS staff as participants by virtue of their professional role. However, the study requires NHS Health Research Authority HRA approval. Before any site can enroll participants

NHS Foundation Trust

into the study, the Chief Investigator/Principal Investigator or designee will ensure that NHS Confirmations of Capacity and Capability and Sponsor green lights are in place.

For any amendments to the study, the Chief Investigator or designee, in agreement with the Sponsor, will submit information to the appropriate body in order for them to issue approval for the amendment. The Chief Investigator or designee will work with sites (R&D departments as well as the study delivery team) to confirm ongoing Capacity and Capability for the study.

All correspondence with the Sponsor and HRA will be retained. The Chief Investigator will notify the Sponsor and HRA of the end of the study.

The final approved study protocol will be registered on OSF Registry (Centre for Open Science).

### **10 COMPLIANCE AND WITHDRAWAL**

#### 10.1 Participant compliance

All participants (whether they consider that they have hand dermatitis or not) will be instructed on how to take photographs of their hands and wrists and upload the photographs on to the REDCap portal within 3 days using a step-by-step instruction guide. Participants who provide photographs that are not sufficiently clear for assessment will be re-contacted and invited to provide an additional set of hand photographs and in order to ensure that the photograph is taken within 3 days of the time as they are being assessed for presence of hand dermatitis, we will require them to re-answer the question *'In your opinion do you have hand/wrist dermatitis/eczema)?'* with answer options of *yes/no or unsure*. Those who answer 'yes', or 'unsure' will then be asked the question: '*where is your hand/wrist dermatitis or skin condition located?*'.

We deem this to be a low-risk study, and we do not anticipate any serious risks by completing the questionnaire. As we have mentioned, by taking part in this study we will collect data from participants including hand photographs and when assessing these, we may detect the presence of hand dermatitis. If this occurs, we will contact participants directly and advise them to self-refer to their local occupational health team as per local arrangements for further management such as advice on suitable work adjustments. In cases where hand dermatitis is detected, the research team will not have the authority to provide any treatment advice and products. Instead, participants will be encouraged to seek treatment advice from your general practitioner or local pharmacy.

#### 10.2 Withdrawal / dropout of participants

Participants will have the option to withdraw from the study at any time without giving a reason. Their\_data will be retained and used in the study unless they express the wish that their responses should be destroyed.

As the data collected by the questionnaire will be identifiable prior to final download from the REDcap database, we can allow participants to withdraw their data after they have submitted the questionnaire, should they desire. Participants will be made aware that they should contact the research team if they would like to withdraw their data. If this occurs, we will use their contact information to identify responses. If an individual did not provide their contact information but would like to withdraw their data, we will use their date of birth and demographic information to identify their record. Participants who did not provide sufficient data required to undoubtedly identify their response will be told that it is not possible to

withdraw their data. Participants will be informed in the PIS that they will not be able to amend their data once their guestionnaire has been submitted.

If participants ask to withdraw their data after their data has been analysed and included in the final analyses, they will then be informed that it will not be possible to remove their data from the study.

#### **10.3 Protocol Compliance**

We consider this to be a low risk study and do not foresee anticipated protocol deviations arising during conduct of this study. Nevertheless, the CI will monitor protocol deviations and list them in a deviation log /include a file note in the TMF/Site file where applicable.

### 11 DATA

#### 11.1 Data to be collected

Pre-consent screening for eligibility questions and participant contact information and questionnaire data will be collected using sponsor approved REDCap software database and access to the source data within the software portal will be password protected and only accessible by authorised persons (i.e. central study team only). This personal identifiable data will be stored on the REDCap software for the duration of the study. However, all downloaded data files from REDCap will have personal identifiable data removed at the point of data extraction and at this point the data file will then become fully pseudonymised and kept in a secure, password file, and only accessible by the study team responsible for conducting the study.

Additionally, the separate personal data extracted at the time of download will be removed from the main data file. Included in this contact information data file will be each participant unique study ID, and this will be used to link participant's contact information back to their response. This will mean that the survey will be pseudonymized for the duration of data analysis and storage. If it is necessary to email data files among research team member, this will be done by sending securely via email in encrypted and password protected data files. Passwords will be sent to the recipient in a separate email.

The following baseline data only will be collected from participants using online tool (REDCap) only. Local managers and research delivery staff will be available to provide practical 1-2-1 assistance with taking and uploading hand photographs in the unlikely event that this should be required.

#### 1. Questionnaire

PART 1

• a) Screening for eligibility (no personal data collected)

• b) Participant Consent Form (Name, email address, preferred telephone number) PART 2

c) Self-assessment questionnaire (Demographic (age in years, gender, ethnicity, skin phototype, occupational group, frequency of hand washing) and self-assessment of hand dermatitis: a single question item about presence/absence of the disease (*'In your opinion do you have hand/wrist dermatitis/eczema*)?' with answer options of *yes/no or unsure*), location of symptoms (tick box of any the options that apply: left (or right) hand palm; left (or right) hand back; left (or right) wrist (front or back); between the fingers; and other part of hand/wrist (e.g. side of hand), with a request to specify the site if this category is selected), duration of symptoms, and level of impact on work, views on the study material and study processes).

PART 3

- Viewing on the study materials and methods (self-assessment of hand dermatitis and taking and sending hand photographs)
- e): Contact details for entry into prize draw (Name, email address and phone number Note: the online questionnaire will be set up such that participants will be required to complete each question before proceeding to the next question.
- 2. Collection of hand photographs

IRAS284234 Digital skin surveillance of healthcare workers in the NHS Protocol v1.0 15.05.25 Page **21** of **30** 

**NHS Foundation Trust** 

 All participants (whether they consider that they have hand dermatitis or not) will be instructed on how to take photographs of their hands and wrists and upload the photographs on to the REDCap portal. Participants will be asked to take one photo each of the front and backs of their hands and wrists using a smartphone following the standardised protocol which was developed and evaluated as part of the SCIN trial. (13) Participants will also be given the option to submit hand photographs to the study team via email.

No follow-up data will be collected from participants.

#### 11.2 Data handling and record keeping

To facilitate data collection, data (completion of the questionnaire and upload of the hand photographs) will be collected using sponsor approved REDCap software database. Access to the source data within the software portal will be password protected and only accessible by authorised members of the study team to aid screening, assessment and scoring of hand photographs and other analyses.

All electronic data will be held securely on Guy's and St Thomas NHS Foundation Trust (GSTT) servers via the REDCap software. The completed REDCap project will be hosted on Amazon Web Services (AWS), a GSTT research and development contracted General Data Protection Regulation (GDPR) compliant third-party storage provider within the Europe (London) region. The pseudonymised research data files will be retained and stored for two years after the completion of the study before being destroyed.

Authorised members of the study team (dermatology nurse and study dermatologists based external to Guy's and St Thomas NHS Foundation Trust 'as sponsor') will have access the password-protected secure online database when undertaking the assessment of the hand photographs. At the end of the study, the pseudonymised data files will be downloaded from REDCap, password protected and securely sent (via email) to [name] the statistician (based at the University of Southampton) to aid final data analyses.

The downloaded data files will be kept in a secure, password file, and only accessible by the study team responsible for conducting the study. Data files will be encrypted and password protected if it is necessary to email data files among research team members e.g. when conducting the data analyses. Passwords will be sent to the recipient in a separate email. Study data will be pseudonymised. Personal data collect in consent form and 'section E: Entry into the prize' of the questionnaire will be stored separate to the study data at the point of download from the REDCap database. Personal data will be deleted within two years of completion of the study.

After site closure, each participating site and collaborating organisation will archive their research data in accordance with instructions from the Sponsor for a period of two years. The process of destroying documents will be in accordance with the standard procedures of the Sponsor.

#### 11.3 Data sharing

The data flow diagram sets out the arrangements for data sharing.

**NHS Foundation Trust** 

At the end of the study and with consent from participants, the final anonymised dataset will be uploaded to OSF data repository for future ethnically approved research. This has been highlighted on the PIS and the ICF, and participants will have the option to with-hold their anonymised data if they desire.

### 11.4 Personal Data Breaches

The CI and study team will comply with the requirements of the UK's data protection law and all data collected as part of this study will strictly be within the terms of the UK GDPR and Data Protection Act 2018. The CI and study team will also adhere, where appropriate, to the current version of the NHS England Code of Practice (Confidentiality). Access to collated participant data will be restricted to the CI and appropriate members of the study team. Computers used to collate the data will have limited access measures via usernames and passwords. Recorded consent will be stored as a datafile on a Guy's and St Thomas NHS Foundation Trust secured shared drive, separate from study data.

Research data will be stored securely in the Occupational Health Service at Guy's and St Thomas NHS Foundation Trust during the study. At the end of the study, data will be archived following the Sponsor's archive standard operating procedure for a period of two year.

Only members of the research team will have access to the personal data details collected using the REDCap database during the study. Access to this database is password restricted. The download file from the REDCap database will be secured stored in access restricted OH Research files on the GSTT servers.

To facilitate the long-term storage of electronic data, data files will be converted to 'read only' before being downloaded onto two encrypted USB sticks. These will be retained in a sealed archive box along with other study documents.

All personal data will be handled and securely stored during the study as outlined above. If there is a data breach/breach of confidentiality (as per GDPR definitions), GSTT Trust incidence reporting mechanisms will be followed. The data subject(s) would also be informed promptly. GSTT Information Governance team will also be immediately informed.

The CI will determine whether the breach meets the definition of a serious breach and warrants reporting to the regulators including the ICO https://ico.org.uk/for-organisations/report-a-breach/personal-data-breach-assessment/.

## MONITORING AND AUDITING

The study will be monitored by the project team which consists of the main study personnel. The CI will oversee the study in collaboration with the study manager with regular input and day-to-day coordination and conduct of the study by remaining members of the study team.

A study-specific Delegation Log will be prepared, detailing the responsibilities of personnel supporting conduct of the study.

The study team will permit study-related monitoring and audit reviews as required. The CI agrees to allow, or representatives (authorised personnel) of the sponsor and external

parties (e.g. regulator), direct access to all study records and source documentation for auditing and compliance purposes where appropriate delegated authority exists.

## **12 STATISTICAL CONSIDERATIONS**

The following outlines the proposed statistical analyses methods planned as they relate to each research question (RQ).

• RQ1 Can a self-assessed hand dermatitis screening questionnaire for at-risk health care workers reliably be used as part of a health surveillance programme?

As the primary study outcome, we will calculate the sensitivity of the proposed selfassessment screening tool (single-item self-reported dermatitis) along with its 95% confidence intervals when compared with the gold standard (nurse's dermatitis assessment from the hand photographs). We will further assess its specificity, positive and negative predictive value. The analysis will be conducted for all participants and then separately by medium and high risk of hand dermatitis, determined by frequency of hand washing 10-20 times per day (medium risk), and more than 20 times per day (high risk).

• RQ2 What is the sensitivity and specificity of the hand dermatitis self-assessment screening questionnaire in identifying early hand dermatitis, and is it similar across all Fitzpatrick skin phototypes and occupational (clinical vs non-clinical) groups?

The accuracy of hand dermatitis self-assessment screening questionnaire will further be explored in sub- groups of our sample participants. Primarily sensitivity, and specificity, and further positive and negative predictive values, as indicators of the accuracy of the screening test will be estimated for clinical and non-clinical staff and their differences will be compared statistically. Due to the high number of NHS staff of non-white ethnic origin, and the lack of information about hand dermatitis or ability to self-report its presence across the six Fitzpatrick skin phototypes, we will also stratify our results by Fitzpatrick phototypes, with a potential to identify skin phototypes in which accuracy of the screening questionnaire is lower.

• RQ3 Is the self-assessment screening questionnaire and photographic method acceptable and feasible to use in healthcare staff in a busy NHS setting?

We will assess this by asking a series of questions relating to the ease with which participants are able to a) complete the self-assessment screening questionnaire and b) follow the instructions for taking and submitting hand photographs. We will set out the response options in Likert scale format to aid analyses of results. We will further ask their willingness to involve their line-managers in the skin surveillance and whether they would accept referral to occupational health if the assessment showed signs of dermatitis. The questionnaire will also include the option for participants to provide further qualitative (free text) feedback on a) reservations about completing the questionnaires and/or uploading photos, b) on barriers and facilitators to implementation of the proposed methods, and c) anything not covered by the questions above. In addition, we will administer a brief case report form to capture feedback from the clinical leads and service managers from the participating departments on the acceptability and feasibility of delivering the skin surveillance method in the clinical setting. We will also enquire about barriers/facilitators of implementing the proposed surveillance method and future practical strategies to optimise its use if this skin health surveillance activity was delegated to them. We will also enquire about existing skin surveillance approaches (if any) at each participating site.

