#### 6.3 Participant exclusion criteria

Individuals with current dermatitis as diagnosed by a medical practitioner, individuals who have used topical steroid cream to their hands in the past six weeks, visiting or temporary personnel who are undertaking duties on NHS premises including students on placements,

NHS Foundation Trust

contractors and anyone not directly employed by the participating NHS organisation. Individuals on long term sick leave (4 weeks or longer)

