Hand photographs (form 3 only) will be accessible to the study nurse via the REDcap portal and the study nurse will assess the presence of dermatitis using the Validated Investigator Global Assessment for Atopic Dermatitis (vIGA-AD) tool (20). Within the portal, the study nurse will then assign and score the photographs to five categories as per IGA score (Category 1: 'Clear'; Category 2: 'Almost clear'; Category 3: 'Mild'; Category 4: 'Moderate'; Category 5: 'Severe') with the first indicating 'absence of dermatitis' and any of the categories 2-5 indicating 'presence of dermatitis'. The dermatology nurse will also keep a separate category for the photographs for which they are unsure and another category for photographs which are insufficiently clear for assessment and which participants will be invited by the research team to resubmit new hand photographs. For the unsure cases, the photographs will be assessed by the dermatologist via the REDcap portal (form 3 only). Information on whether participants' hand photographs require further assessment by the study dermatologist (i.e. categorised as 'Unsure' by the study nurse) will also be recorded in REDcap, as it is relevant for future application of surveillance method.

Participants who provide photographs that are not sufficiently clear for assessment will be recontacted by a member of the central study team (not the study dermatologists or dermatology nurse) and invited on one occasion only to provide an additional set of hand photographs. In order to ensure that the photograph is taken within 3 days of the time as they are being assessed for presence of hand dermatitis, we will require them to re-answer the question *'In your opinion do you have hand/wrist dermatitis/eczema)?'* with answer options of *yes/no or unsure*. Those who answer 'yes', or 'unsure' will then be asked the question:

'*where is your hand/wrist dermatitis or skin condition located?*'. A separate form (form 6) will be used to collect re-submitted hand photographs. Photographs that the dermatology nurse deems to be of too poor quality to assess will not be included in the final analysis.

Prior to assessing the presence of dermatitis, to ensure appropriate use of the vIGA-AD tool, the dermatologist nurse will be required to complete a training consisting of a video on best practices for using the scale to rate the severity of the disease and subsequently complete a certification examination as described by Simpson et al. (20)

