Once the study nurse is fully trained, they will independently assess all hand photographs. After nurse's assessment has been completed, the presence or absence of dermatitis (vIGA score Categories 2-5 and Category 1, respectively) will be compared with participants' self-responses.

Photographs on discordant pairs (outcomes 2 and 3 described below) will be further assessed by the two study dermatologists who will assess presence of dermatitis. The dermatologist will independently assess the hand photographs for presence of hand dermatitis and score 1-5 on the vIGA scale. If the dermatologists' scores differ they will agree a score by discussion. The original nurse's assessment using the vIGA tool will be corrected for the dermatologists' expert opinion where needed.

The nurse's assessment of the hand photographs and any back up required by the study dermatologist with correction of the assessment on the vIGA scale where needed, will be considered the gold standard against which the questionnaire-based self-assessed presence of dermatitis (new proposed screening tool) will be compared. We will assess the acceptability of the self-assessment screening tool by incorporating several short questions into the study questionnaires.

The questionnaire we will also include several questions to capture participants views on the study material, and the instructions they have to follow to complete the self-assessment screening questionnaire and for taking and submitting hand photographs. Response options will be set out in Likert scale format to aid analyses of results. We will further ask their willingness to involve their line-managers in the skin surveillance. The questionnaire will also include the option for participants to provide further qualitative (free text) feedback on a) concerns about completing the questionnaires and/or uploading photos, b) on obstacles and facilitators to implementation of the proposed methods, and c) anything not covered by the questions above.

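### RQ2 asks about accuracy for early hand dermatitis, but the planned analysis estimates sensitivity for dermatitis of any severity

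*Protocol*

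**What the plan says.** The synopsis, section 4.1 and section 12 of the protocol all pose RQ2 as the "sensitivity and specificity of the hand dermatitis self-assessment screening questionnaire in identifying early hand dermatitis", and ask whether it is similar across skin phototypes and across clinical and non-clinical staff. No section defines *early*.

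Section 7.3 has each photograph graded in five vIGA categories, from clear (1) to severe (5), with "any of the categories 2-5 indicating 'presence of dermatitis". The comparison is then binary: "the presence or absence of dermatitis (vIGA score Categories 2-5 and Category 1, respectively) will be compared with participants' self-responses". The four outcomes in section 7.4 use the same present/absent split.

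Section 12 names its breakdowns. For RQ1 the analysis is run overall and "separately by medium and high risk of hand dermatitis, determined by frequency of hand washing". For RQ2 the accuracy measures "will be estimated for clinical and non-clinical staff and their differences will be compared statistically", and "we will also stratify our results by Fitzpatrick phototypes". No analysis is by vIGA category or by duration.

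Two other passages matter. Section 6.3 excludes "Individuals with current dermatitis as diagnosed by a medical practitioner", people who have used topical steroid on the hands in the past six weeks, and staff on long-term sick leave. Section 11.1 lists "duration of symptoms, and level of impact on work" among the questionnaire items.

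**The concern.** Early detection is the reason given for the study. The Introduction says that dermatitis in health service staff is often found late, when it is harder to treat, and section 17.1.1 rests the case for wider adoption on earlier detection. The planned RQ2 estimate does not isolate early disease. A participant with severe undiagnosed dermatitis who answers yes counts towards sensitivity exactly as one with faint first signs does. If established disease is easier to self-recognise, the pooled figure overstates how well the question finds early disease, and the report could claim an early-detection property that was never estimated.

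The comparisons between staff groups and phototypes share the weakness. If the mix of severities differs between groups, a difference in pooled sensitivity may reflect that mix and not how well people in each group recognise a given degree of disease.

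**Working it through.** **1. The plan's own figure.** Inputs from section 12.1: prevalence 0.15, expected sensitivity 0.90 (printed as a percentage, read as a proportion), precision 0.10, 95% two-sided.

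- Cases needed = 1.96² × 0.90 × 0.10 / 0.10² = 34.57.
- Participants per group = 34.57 / 0.15 = 230.5, rounded up to 231. Six groups give 6 × 231 = 1386.

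The figure reproduces with 0.10 as a half-width; as a full width it would be 922 per group. The prevalence is for any hand dermatitis, so 231 and 1386 are sized for pooled sensitivity. Expected cases: 0.15 × 1386 = 207.9, about 208, or 34.65 per group.

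**2. What pooled sensitivity says about early disease.** Let *s* be the share of category 2–5 cases that are early. Then

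pooled Se = *s* × Se(early) + (1 − *s*) × Se(later), so Se(early) = [pooled Se − (1 − *s*) × Se(later)] / *s*.

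The pooled value is set at the protocol's 0.90. The protocol gives neither *s* nor Se(later); both are assumed and varied.

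| Early share *s* | Se(early) if Se(later) = 1.00 | if 0.98 | if 0.95 |
|---|---|---|---|
| 30% | 0.67 | 0.71 | 0.78 |
| 50% | 0.80 | 0.82 | 0.85 |
| 70% | 0.86 | 0.87 | 0.88 |
| 90% | 0.89 | 0.89 | 0.89 |

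Example: (0.90 − 0.70 × 0.98) / 0.30 = 0.214 / 0.30 = 0.71. The gap is large when early cases are a minority and negligible when they are nearly all the cases.

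**3. Group comparisons.** Assume Se(early) = 0.80 and Se(later) = 0.98 in both of two groups. With 30% early cases the pooled value is 0.30 × 0.80 + 0.70 × 0.98 = 0.926. With 70% it is 0.70 × 0.80 + 0.30 × 0.98 = 0.854. Severity mix alone produces an apparent difference of 0.07. This shows what could happen; it is not a forecast.

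**4. Precision of an early-disease estimate.** Half-width = 1.96 × √(0.90 × 0.10 / n), with n = 208 × *s* overall and one sixth of that per group.

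| *s* | Early cases overall | Half-width | Early cases per group | Half-width |
|---|---|---|---|---|
| 30% | 62 | 0.074 | 10.4 | 0.182 |
| 50% | 104 | 0.058 | 17.3 | 0.141 |
| 70% | 146 | 0.049 | 24.3 | 0.119 |
| 90% | 187 | 0.043 | 31.2 | 0.105 |

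A whole-sample estimate is feasible. Within each of the six groups it misses the planned 0.10 at every share tried. These widths hold at sensitivity 0.90; at 0.71 with 62.4 cases the overall half-width is 1.96 × √(0.71 × 0.29 / 62.4) = 0.11.

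**5. Specificity.** Its denominator is category 1 only, so severity mix among cases does not enter it.

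**The case against.** The best defence is that the design already leans towards early disease. Section 6.3 removes diagnosed and recently treated dermatitis and staff on long-term sick leave, and section 7.3 counts even almost-clear skin as positive. Undiagnosed, untreated disease at the lowest visible threshold is a plausible meaning of *early*. This stands in part: the spectrum is narrowed. But the protocol never equates undiagnosed with early, and undiagnosed moderate or severe cases still count as positive.

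Severity is also not the same as earliness, since a mild case can be long-standing. That is right, and it limits any vIGA-based definition to a proxy. Symptom duration is collected, but the protocol does not say how it is recorded for people who answer no, and they include the false negatives. A vIGA grade exists for every assessable case.

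A breakdown by severity could be left to a statistical analysis plan, which is not shown. Here, however, the protocol itself fixes the cut-off and sets out the analysis for each research question, so the mismatch lies within the document.

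A reader might go further and infer three things that the text does not support:

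- **That the primary outcome is mis-specified.** RQ1 does not mention early disease, and the 80% minimum in section 12.1 was elicited for detecting hand dermatitis generally. Pooled sensitivity in the surveillance population is a proper target there.
- **That severity mix will differ between groups.** The protocol gives no severity distribution; a difference is possible, not established.
- **That the analysis should be repeated with presence set at category 3 or above, or that group comparisons need adjustment for vIGA.** The first drops the faintest disease and so does not serve an early-disease question. The second conditions on a grade that may itself vary with phototype, given the recognition difficulties that the Introduction describes, and section 12 specifies no model to hold such a term.

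**Conclusion.** The point holds as a mismatch between question and analysis, confined to RQ2. The planned result is sensitivity for any dermatitis among staff without a current medical diagnosis of it, and it cannot be read as sensitivity for early dermatitis.

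How much this matters depends on a share that the documents do not give. With pooled sensitivity 0.90 and 0.98 assumed in later disease, early-disease sensitivity runs from 0.71 at a 30% early share to 0.89 at 90%. If nearly all cases are early, the practical consequence is small. The illustration also assumes that later disease is self-recognised more readily than early disease, which the protocol does not quantify. RQ1, its primary outcome and the sample size calculation are not affected.

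**What to change.** In section 12, under RQ2:

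1. State before analysis how *early* is operationalised, for example as vIGA categories 2–3, and acknowledge that severity is only a proxy for earliness.
2. Report sensitivity with 95% CI by vIGA category (2, 3, and 4–5) in the whole sample.
3. Show the vIGA distribution of cases by staff group and by phototype beside the group comparisons, so that differences that may reflect severity mix are visible.

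Alternatively, remove *early* from RQ2 wherever it is posed and limit the conclusion to any dermatitis. Either way, keep pooled sensitivity as the RQ1 primary outcome.

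The cost is one or two extra tables from scores already recorded. Intervals will be wide, so the breakdown should be descriptive and not repeated within the six groups. The report also needs a caveat about grading. Under sections 7.3 and 7.4 the dermatologists re-grade only discordant and nurse-unsure photographs. False negatives therefore carry a dermatologist grade, while true positives on which nurse and participant agree normally keep the nurse's. Category-specific sensitivity thus sets cases graded by different assessors against each other.
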